#### **4.8 Interruption or Discontinuation of Study Dosing and Entry**

If any of the following occur, no further administration of investigational product will take place and no further subjects will be entered into the study:

- 1) Death in any subject in which the cause of death is assessed as possibly, probably, or definitely related to investigational product;
- 2) Anaphylactic reaction to investigational product in any subject; or
- 3) Other events that, in the judgment of the medical monitor, are serious enough to warrant immediate review by the sponsor Safety Monitoring Committee (SMC).

If one of the above-listed events occurs, a prompt cumulative review of safety data and the circumstances of the event in question will be conducted by the medical monitor and the SMC to determine whether dosing and study entry should be resumed, whether the protocol will be modified, or whether the study will be discontinued permanently. Review and approval by the SMC are required for resumption of the study in the event the study is interrupted because of one of the above-listed events.

#### **4.9 Dose Escalation**

Rules for dose escalation are as follows:

- 1) Subjects enrolled in Dose Cohort 1 (3.0 mg/kg) only will receive a single, lead-in dose of MEDI-575 at 0.5 mg/kg administered 7 days prior to receipt of the first dose of MEDI-575 at the 3.0 mg/kg dose level. The DLT period for this dose cohort only will begin with the single administration of MEDI-575 at the dose level of 0.5 mg/kg (Study Day 1) and continue until 21 days after the administration of the first dose of MEDI-575 at the 3.0 mg/kg dose level (Study Day 28). Any DLTs that occur in subjects in this cohort after the administration of the lead-in dose, but prior to

administration of the first dose at the 3.0 mg/kg dose level will be considered related to the 0.5 mg/kg dose. DLTs that occur after MEDI-575 has been administered at a dose of 3.0 mg/kg will be considered related to the 3.0 mg/kg dose. Dose escalation and administration of investigational product for this and all subsequent cohorts will follow the rules outlined below.

- 2) Dose escalation will begin with a single subject in each dose cohort. If no DLTs (as defined in Section 4.10) are observed in this subject within the first 7 days of administration of MEDI-575, 2 additional subjects will be enrolled into that dose cohort and may be dosed immediately.
- 3) If no DLTs are observed in the first 3 subjects treated in the dose cohort through the first 28 days (Dose Cohort 1) or 21 days (Dose Cohort 2 and above) of administration of MEDI-575, enrollment into the next higher dose cohort will begin using the same rules described in Item 2.
- 4) If 1 out of 3 subjects within a dose cohort experiences a DLT, that dose cohort will be expanded to a total of 6 subjects provided no further subjects experience a DLT. If no further subjects experience a DLT through the first 28 days (Dose Cohort 1) or 21 days (Dose Cohort 2 and above) of administration of MEDI-575 in the expanded dose cohort, dose escalation will continue in the next higher dose cohort using the same rules described in Item 2.
- 5) If 2 or more subjects within a dose cohort experience a DLT within the first 28 days (Dose Cohort 1) or 21 days (Dose Cohort 2 and above) of administration of MEDI-575, then the MTD will be exceeded and no further subjects will be enrolled into that dose cohort. If this happens, the preceding dose cohort will be evaluated as the MTD, with the addition of 3 subjects if this dose cohort has not previously been expanded to 6 subjects. If  $\leq 1$  of 6 subjects experiences a DLT, this dose will be declared the MTD. Approximately 6 additional subjects will be enrolled into the MTD dose cohort as well as the dose cohort below the MTD dose cohort to evaluate PK and pharmacodynamic parameters and determine tumor response.
- 6) If the MTD is not reached at a dose of 15 mg/kg/week, a dose will be determined from Cohorts 1 through 5 using a combination of PK, pharmacodynamic markers, safety, and when available, efficacy data. The maximum dose for the weekly schedule will be 15 mg/kg. This weekly dose level will be used in the dose-expansion phase as the weekly dose-expansion dose. Two additional cohorts will also be added at 25 mg/kg (Dose Cohort 6) and 35 mg/kg (Dose Cohort 7) administered as a 90-minute IV infusion once every 21 days (on Study Day 1) to the dose-escalation phase. One of these doses (based on PK, pharmacodynamic markers, safety, and, when available, efficacy data) will be used in the dose-expansion phase as the every 3-week expansion dose. The subjects enrolled in Cohorts 6 and 7 will be evaluated identically to subjects in Cohorts 1 through 5 in the dose-escalation phase. The decision to escalate from 25 mg/kg to 35 mg/kg will be made using the same parameters as those used for the weekly dosing schedule.

- 7) The dose-expansion phase will consist of approximately 12 subjects. Approximately 6 subjects will be treated once every 7 days of a 21-day cycle (weekly schedule) at a dose identified by the criteria in Item 6 from Cohorts 1 through 5. Another 6 subjects will be treated once every 21 days on Study Day 1 (every 3-week schedule) at a dose identified by the criteria in Item 6 from Cohorts 6 and 7. The subjects in these dose-expansion cohorts must have one of the following advanced solid tumors: NSCLC, GBM, ovarian cancer, or synovial sarcoma.
- 8) At the discretion of the sponsor, an intermediate dose may be chosen for dose escalation. Situations which might prompt selection of an intermediate dose include unexpected toxicities that do not meet the definition of DLT or multiple similar toxicities in a cohort that do not meet the definition of a DLT. If an intermediate dose is chosen, dose escalation will be to the next listed dose provided all the criteria for dose escalation in Items 2 through 4 above are met. Further escalation will be based on toxicities observed at each dose level, and may proceed on the original schedule or include additional intermediate steps based on accumulated safety data.

The decision to enroll the next higher dose cohort or to continue enrollment in the current dose cohort will be based on review of safety data following the proscribed observation period. The decision will be jointly made following a meeting or teleconference attended by all investigators, the medical monitor, a MedImmune Patient Safety physician, and the therapeutic area head (optional). A representative from clinical operations will document the discussion and decision. Treating investigators will provide a verbal or written summary of treatment including description of any AEs. If a treating investigator is unable to attend, a written summary of findings will be submitted. A decision will not be reached unless all treating physicians have attended the meeting or teleconference or submitted a written summary. Dose escalation will not proceed until approved by the sponsor.

At the discretion of the sponsor, the dosing interval may be increased from once every 7 days to once every 14 days or longer at a dose or doses at or below the MTD. This decision will be based on accumulated PK, pharmacodynamic markers, tumor response, and safety data. Administration of investigational product and dose escalation may continue on a weekly schedule concurrently with dose escalation using an increased dosing interval. The maximum dose administered will be 15 mg/kg per dose.

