Dose escalation will follow a standard 3+3 study design. Rules for dose escalation are described in Section 4.9.

For the dose-expansion phase, approximately 12 subjects may be enrolled. All 12 subjects enrolled in the dose-expansion phase must have one of the following advanced solid tumors: NSCLC, GBM, ovarian cancer, or synovial sarcoma. The subjects in the dose-expansion phase will be evaluated identically to the other subjects during the dose-escalation phase. In the dose-expansion phase, 6 subjects will be treated once every 7 days of a 21-day cycle (weekly schedule) as a 60-minute IV infusion at a dose to be determined based on an analysis of PK, pharmacodynamic markers, and safety from Cohorts 1 through 5. Another 6 subjects will be treated at a dose of either 25 or 35 mg/kg once every 21 days beginning on Study Day 1 (every 3-week schedule) as a 90-minute IV infusion based on an analysis of PK, pharmacodynamic markers, and safety from Cohorts 6 and 7. The 25 or 35 mg/kg dose will be pursued pending no significant safety findings at these doses during the dose-escalation phase (Cohorts 6 and 7). Enrollment in the weekly dose-expansion schedule can occur simultaneously with Cohorts 6 and 7. Subjects will be enrolled in the every 3-week dose-expansion schedule once Cohorts 6 and 7 are complete and a choice of dose is made as described above.

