### **5.2 Sample Size**

For the dose escalation phase, a minimum of 21 evaluable subjects (3 subjects in Dose Cohorts 1 through 7) or up to approximately 42 evaluable subjects (3+3 subjects per dose cohort) will be required to determine the MTD. A subject will be considered evaluable if the subject receives at least 1 full cycle of MEDI-575 and completes the safety follow-up through the DLT evaluation period, or the subject experiences a DLT. Any non-evaluable subject will be replaced in the same dose cohort.

For the dose-expansion phase, approximately 12 subjects may be entered; approximately 6 subjects at a dose to be determined from Dose Cohorts 1 through 5 (weekly schedule) and approximately 6 subjects at a dose to be determined from Dose Cohorts 6 and 7 (every 3-week schedule).

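### Section 4.9 Item 5 does not confine the preceding cohort or the cohort below to the same schedule, so a Cohort 6 failure literally sends the MTD evaluation to weekly Cohort 5

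*Protocol*

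**What the plan says.** Determining the MTD and/or optimal biologic dose is a primary objective (Section 2.1), and Section 5.4 refers the determination of the MTD to Section 4.9.

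- **Scope.** Item 1 of Section 4.9 states: "Dose escalation and administration of investigational product for this and all subsequent cohorts will follow the rules outlined below". Item 5 gives its 21-day window for Cohort 2 and every cohort above it. Item 6 adds: "The subjects enrolled in Cohorts 6 and 7 will be evaluated identically to subjects in Cohorts 1 through 5 in the dose-escalation phase".
- **Stop and fallback.** With 2 or more DLTs in a cohort, Item 5 says "then the MTD will be exceeded and no further subjects will be enrolled into that dose cohort". It continues: "If this happens, the preceding dose cohort will be evaluated as the MTD". Three subjects are added there if that cohort has not already been expanded to 6, and the dose is declared the MTD if at most 1 of 6 has a DLT. Then: "Approximately 6 additional subjects will be enrolled into the MTD dose cohort as well as the dose cohort below the MTD dose cohort".
- **Schedules.** In Table 3.5.2-1, Cohorts 1 to 5 are weekly, with Cohort 5 at 15 mg/kg every 7 days. Cohorts 6 and 7 receive 25 and 35 mg/kg every 21 days. The numbering is one sequence.
- **Link between schedules.** Item 6 starts from the case in which the MTD is not reached at 15 mg/kg weekly. A weekly expansion dose is then chosen from Cohorts 1 to 5, and Cohorts 6 and 7 are added. The Study Design text says: "Enrollment in the weekly dose-expansion schedule can occur simultaneously with Cohorts 6 and 7".
- **Sample size.** Section 5.2 says that "up to approximately 42 evaluable subjects (3+3 subjects per dose cohort) will be required to determine the MTD", without separating the schedules.
- **Longer intervals.** The last paragraph of Section 4.9 says "the dosing interval may be increased from once every 7 days to once every 14 days or longer at a dose or doses". It restricts this option to doses that do not exceed the MTD and sets a ceiling of 15 mg/kg for each dose.

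**The concern.** A 3+3 fallback assumes that the preceding cohort is a step down on the same dose scale. That is true within Cohorts 1 to 5 and between Cohorts 6 and 7. It is not true between Cohorts 5 and 6, where dose and schedule change together. Item 5 covers that join and says nothing about schedule.

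What is at stake is the label attached to a primary objective. Toxicity on the every-3-week schedule could lead to 15 mg/kg weekly being declared the MTD. Item 6 treats that dose as one at which the MTD was not reached, and the weekly expansion may already be enrolling at a weekly dose chosen on that footing. The rule could also add weekly subjects on the strength of every-3-week findings.

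**Working it through.** **1. The plan's own figures.** Section 5.2 gives 21 to about 42 evaluable subjects. 7 cohorts × 3 = 21 and 7 × 6 = 42, so both reproduce. They confirm that all seven cohorts are counted together towards the MTD.

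**2. Does Item 5 reach Cohorts 6 and 7?** Yes, by three routes: Item 1 (all subsequent cohorts), Item 5 (Cohort 2 and above) and Item 6 (identical evaluation).

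**3. Is the fallback a step down?** Dose per 21 days = dose per infusion × infusions in 21 days (regimens from Table 3.5.2-1).

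| Cohort | mg/kg per infusion | infusions in 21 days | mg/kg per 21 days |
|---|---|---|---|
| 5 | 15 | 3 | 45 |
| 6 | 25 | 1 | 25 |
| 7 | 35 | 1 | 35 |

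From Cohort 6 to Cohort 5 the dose per infusion falls (15/25 = 0.6), but the dose over the 21-day DLT period rises (45/25 = 1.8). Cohort 5 also exceeds Cohort 7 over 21 days (45 against 35). The order of the regimens depends on the measure used, so Cohort 5 is not a valid step down from Cohort 6.

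**4. The two branches, read literally.**

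- *Cohort 6 has 2 or more DLTs.* 25 mg/kg every 21 days is stopped, correctly. The MTD evaluation then moves to Cohort 5, which can be declared the MTD.
- *Cohort 7 has 2 or more DLTs.* The evaluation moves to Cohort 6, correctly. If Cohort 6 is declared the MTD, the cohort below it, which receives about 6 more subjects, is Cohort 5.

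**5. How likely is the Cohort 6 branch?** The protocol gives no DLT rate, so p is assumed. A cohort passes with 0 of 3 DLTs, or with 1 of 3 followed by 0 of 3:

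F(p) = 1 − [(1−p)³ + 3p(1−p)⁵]

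- p = 0.05: 1 − (0.8574 + 0.1161) = 0.0266
- p = 0.10: 1 − (0.7290 + 0.1771) = 0.0939

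Assume Cohort 5 closed with 0 of 3 and has the same rate. It is then declared the MTD if at most 1 of 3 added subjects has a DLT:

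M(p) = (1−p)³ + 3p(1−p)²

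- p = 0.05: 0.8574 + 0.1354 = 0.9927; joint F × M = 0.0264
- p = 0.10: 0.7290 + 0.2430 = 0.9720; joint F × M = 0.0912

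At these rates nearly every Cohort 6 failure would end with weekly Cohort 5 labelled the MTD.

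**6. Which rates are plausible?** Section 2.4 reports no DLTs in the first five cohorts. Assuming 3 subjects in each (15 in all) and one common rate, the chance of 0 of 15 is 0.95¹⁵ = 46% at 5%, 0.90¹⁵ = 21% at 10%, 0.80¹⁵ = 3.5% at 20% and (2/3)¹⁵ = 0.2% at 33%. This favours the lower rates, although the weekly cohorts do not measure the rate on the other schedule.

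**The case against.** **The same-ladder reading.** Item 6 treats the weekly ladder as closed without an MTD, sets a separate weekly maximum and describes 25 to 35 mg/kg as its own escalation. Items 6 and 7 also choose the two expansion doses separately. A sensible team would read the preceding cohort as the one on the same schedule. This reading is reasonable, but no text shown states it, and it leaves Cohort 6 with no predecessor and Item 5 with no instruction. Item 8 does not fill that gap: it lets the sponsor choose an intermediate dose during escalation, at its discretion.

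**Oversight.** Cohort decisions go to a joint meeting with sponsor approval, and the Safety Monitoring Committee reviews them. This makes mechanical misapplication less likely, but it does not change the rule.

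**Figure 2.4-1.** The flow diagram covers exactly Cohorts 1 to 7 and was not available. It may show a path for a Cohort 6 failure, which is a real limit on this point.

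**Stronger readings that the documents do not support.**

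- *That the stopping rule fails, or that subjects go to an uncleared regimen.* Item 5 does stop 25 mg/kg every 21 days, and under Item 6 Cohort 5 would already have passed. The ratio of 1.8 is one of administered dose. It does not show that Cohort 5 is more toxic.
- *That the expansion doses are corrupted.* Items 6 and 7 set them per schedule, and Section 2.4 makes the every-3-week expansion conditional on no significant safety findings in Cohorts 6 and 7.
- *That the branch is common.* The same formula gives 29% at a 20% rate and 57% at 33%, but those rates fit poorly with no DLTs in five cohorts.
- *That about 15 unplanned weekly subjects follow (3 + 6 + 6).* Three of these lie within the planned cohort size of 3 to 6, and up to about 6 may overlap the weekly expansion. The enrollment of about 6 in each of two cohorts is a general feature of Item 5, not a product of mixing schedules.
- *That the Cohort 7 branch picks the wrong MTD.* It does not; only the cohort below is misdirected.

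**Conclusion.** The point holds in limited form and should be fixed. Item 5 governs Cohorts 6 and 7 without a schedule limit. Followed literally, a Cohort 6 failure moves the MTD evaluation to a weekly regimen that is lower per infusion but 1.8 times higher per 21 days, and can declare it the MTD although no weekly cohort exceeded the limit. A Cohort 7 failure misdirects only the additional enrollment in the cohort below.

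The consequence is mainly a wrong label on a primary objective, with some weekly enrollment justified by it. It arises with probability about 3% to 9% at assumed DLT rates of 5% to 10%. The conclusion about the wording does not depend on those rates. It does depend on Figure 2.4-1 containing no contrary instruction, which could not be checked.

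**What to change.** Amend Section 4.9 Item 5:

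1. State that the preceding dose cohort and the dose cohort below mean cohorts on the same schedule, and that the MTD is determined separately for the weekly and every-3-week schedules.
2. Add the Cohort 6 case. With 2 or more DLTs, 25 mg/kg every 21 days exceeds the every-3-week MTD. Cohort 7 and the every-3-week expansion at 25 or 35 mg/kg do not open, and Cohort 5 is not re-evaluated as the MTD on that basis. Any lower every-3-week dose above 15 mg/kg needs a protocol amendment, because the interval-extension provision is capped at 15 mg/kg per dose.
3. Add the Cohort 7 case. With 2 or more DLTs, Cohort 6 is evaluated as the every-3-week MTD, and no weekly cohort is expanded as the cohort below.

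Check Figure 2.4-1 for consistency. No separate change to Section 5.4 is needed: it refers to Section 4.9 for the MTD and already summarizes DLTs by cohort, and each numbered cohort has a single schedule.

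The cost is a short wording amendment. The 21 to about 42 evaluable escalation subjects and the approximately 12 expansion subjects are unchanged, unless a lower every-3-week cohort is later added by amendment.

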#### **4.10 Definitions of Dose-limiting Toxicities**

Dose-limiting toxicities will be graded according to the NCI CTCAE V3.0. The DLT period for Dose Cohort 1 only will begin with the single lead-in administration of MEDI-575 at the dose level of 0.5 mg/kg (Cycle 1, Study Day 1) and continue through the entire first cycle of treatment (Cycle 1, Study Day 28) for a total of 28 days. The DLT period for Dose Cohorts 2

through 7 will begin with the administration of the first dose of MEDI-575 and continue through the entire first cycle of treatment (Cycle 1, Study Day 1 through Cycle 1, Study Day 21).

A DLT is defined as:

- 1) Any Grade 3 or higher non-hematologic toxicity that occurs during the DLT assessment period where a cause other than the investigational product (such as disease progression or accident) cannot be reasonably justified with the following exceptions:
  - Grade 3 fever (in the absence of neutropenia) defined as  $> 40.0^{\circ}\text{C}$  ( $>104.0^{\circ}\text{F}$ ) that resolves to normal or baseline within 24 hours of treatment and is not considered an SAE; or
  - Grade 3 rigors/chills that respond to optimal therapy.
- 2) Any Grade 3 or higher hematologic toxicity where a cause other than the investigational product (such as disease progression or accident) cannot be reasonably justified.

## **5 Statistical Considerations**

### **5.1 General Considerations**

The analysis of study data is the responsibility of MedImmune or its designee. A comprehensive statistical analysis plan will be approved prior to the analysis of study data.

All data will be provided in data listings sorted by dose cohort. Continuous variables will be summarized by descriptive statistics including N, mean, standard deviation, median, and range. Descriptive statistics for summarizing categorical variables include frequency and percentage. Missing data will be treated as missing and no data will be imputed.

### **5.2 Sample Size**

For the dose escalation phase, a minimum of 21 evaluable subjects (3 subjects in Dose Cohorts 1 through 7) or up to approximately 42 evaluable subjects (3+3 subjects per dose cohort) will be required to determine the MTD. A subject will be considered evaluable if the subject receives at least 1 full cycle of MEDI-575 and completes the safety follow-up through the DLT evaluation period, or the subject experiences a DLT. Any non-evaluable subject will be replaced in the same dose cohort.

For the dose-expansion phase, approximately 12 subjects may be entered; approximately 6 subjects at a dose to be determined from Dose Cohorts 1 through 5 (weekly schedule) and approximately 6 subjects at a dose to be determined from Dose Cohorts 6 and 7 (every 3-week schedule).

### **5.3 Analysis Populations**

The safety population will include all subjects who receive any MEDI-575.

The evaluable population for MTD is defined as all those subjects who receive at least 1 full cycle of MEDI-575 and complete the safety follow-up through the DLT evaluation period, or who experience a DLT.

### **5.4 Primary Endpoints**

The primary objectives of this study are to evaluate the safety and tolerability of MEDI-575 in adult subjects with advanced solid tumors refractory to standard therapy or for which no standard therapy exists and to determine the MTD and/or optimal biological dose of MEDI-575 in this subject population. All safety endpoints will be summarized descriptively. Adverse events and SAEs will be summarized by dose cohort, system organ class, severity, and relationship to MEDI-575 through 30 days after the last dose of MEDI-575.

Determination of the MTD is described in Section 4.9 and descriptive statistics will be provided to summarize the occurrence of DLTs by dose cohort.

### **5.5 Secondary Endpoints**

Secondary endpoints include assessments of PK, IM, and antitumor activity of MEDI-575.

#### **5.5.1 Pharmacokinetics of MEDI-575**

The PK of MEDI-575 will be assessed using the variables of AUC, (which will be calculated by the trapezoidal rule),  $C_{\max}$ ,  $T_{\max}$ ,  $t_{1/2}$ , and CL. These parameters will be obtained by non-compartmental methods. Linearity in the PK of MEDI-575 will be assessed from  $t_{1/2}$  and dose-normalized AUC and  $C_{\max}$ . Descriptive statistics will be provided by dose cohort.

### **5.5.2 Immunogenicity of MEDI-575**

Immunogenicity of MEDI-575 will be assessed and summarized descriptively by dose cohort.

### **5.5.3 Antitumor Activity of MEDI-575**

The antitumor activity of MEDI-575 will be assessed based on ORR, TTR, DR, TTP, PFS, and OS.

The ORR is defined as the proportion of subjects with confirmed CR or confirmed PR according to RECIST guidelines. Confirmed responses are those that persist on repeat imaging study  $\geq 4$  weeks after the initial documentation of response.

The TTR will be measured from the start of treatment with MEDI-575 to the first documentation of objective response and will only be assessed in subjects who have achieved objective response.

The DR will be defined as the duration from the first documentation of objective response to the first documented disease progression. The DR will be censored on the date of last tumor assessment documenting absence of disease progression for subjects who have no documented progression prior to data cutoff, dropout, or the initiation of alternate anticancer therapy. The DR will only be calculated for the subgroup of subjects with an objective response.

The TTP will be measured from the start of treatment with MEDI-575 until the documentation of disease progression. Disease progression is defined according to RECIST guidelines. The TTP will be censored on the date of last tumor assessment documenting absence of tumor progression for subjects who have no documented progression prior to data cutoff, dropout, or the initiation of alternate anticancer therapy. Subjects having no tumor assessments after the start of treatment with MEDI-575 will have TTP censored on the first date of treatment with MEDI-575.

The PFS will be measured from the start of treatment with MEDI-575 until the documentation of disease progression or death due to any cause, whichever occurs first. Disease progression is defined according to RECIST guidelines. The PFS will be censored on the date of last tumor assessment documenting absence of tumor progression for subjects who have no documented progression and are still alive prior to data cutoff, dropout, or the initiation of alternate anticancer therapy. Subjects having no tumor assessments after the start

of treatment with MEDI-575 will have PFS censored on the first date of treatment with MEDI-575.

The OS will be determined as the time from the start of treatment with MEDI-575 until death. For subjects who are alive at the end of study or lost to follow-up, OS will be censored on the last date when subjects are known to be alive.

The time to event data, including TTR, DR, TTP, PFS, and OS, will be evaluated using Kaplan-Meier methods.

A selected panel of biomarkers will be employed which may include evaluation of the effects of MEDI-575 on serum tumor biomarkers including PSA and CA-125, or other tumor markers as determined by tumor type. Descriptive statistics will also be provided.

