**Cycle 2 and All Subsequent Cycles, Study Day 15 (Cohorts 1 through 5 and Weekly Dose-Expansion)**

- 1) Update concomitant medications
- 2) Blood collection prior to infusion of MEDI-575

- Chemistry panel (AST/ALT, total bilirubin, creatinine, alkaline phosphatase, sodium, potassium, chloride, phosphorus, calcium, glucose, magnesium, albumin, and LDH)
  - Hematology (CBC, differential, and platelet count)
  - Serum concentration of MEDI-575
  - Circulating plasma biomarker analysis
- 3) Routine urinalysis
  - 4) Vital signs prior to infusion of MEDI-575 (temperature, blood pressure, pulse rate, respiratory rate)
  - 5) Administration of MEDI-575
  - 6) Assessment of AEs and SAEs
  - 7) Monitor vital signs at 15, 30, and 45 minutes ( $\pm$  5 minutes) post initiation of infusion, at the completion of infusion ( $\pm$  5 minutes), and 30 and 60 minutes ( $\pm$  5 minutes) post completion of infusion
  - 8) Blood collection immediately after ( $\pm$  5 minutes) completion of infusion of MEDI-575
    - Serum concentration of MEDI-575
    - Circulating plasma biomarker analysis

**Every 2 Cycles (Within 3 Days Prior to Subsequent Cycle, Beginning With Cycle 3; All Dose Cohorts and Dose-Expansion Phase)**

*The following evaluations will be performed every 2 cycles (ie, every 6 weeks) unless otherwise indicated, beginning at Cycle 3 (eg, Cycle 3, Cycle 5, etc)*

- 1) Complete physical examination
- 2) Update concomitant medications
- 3) Assess for AEs and SAEs
- 4) Evaluation of disease
  - CT or MRI scans
  - Focused physical examination

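### Duration of response ends only at documented progression, so a responder's death is censored; any reported probability of progression should treat death as a competing event

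*Protocol*

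**What the plan says.** For DR, Section 5.5.3 makes progression the only event: "The DR will be defined as the duration from the first documentation of objective response to the first documented disease progression". The censoring rule follows: "The DR will be censored on the date of last tumor assessment documenting absence of disease progression for subjects who have no documented progression" before data cutoff, dropout or new anticancer therapy. TTP has the same form: "The TTP will be measured from the start of treatment with MEDI-575 until the documentation of disease progression", and then "The TTP will be censored on the date of last tumor assessment documenting absence of tumor progression for subjects who have no documented progression" before the same three points. Neither rule mentions death.

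PFS, in the same section, does. It runs "until the documentation of disease progression or death due to any cause, whichever occurs first", and its main censoring rule is limited to subjects "who have no documented progression and are still alive prior to data cutoff, dropout, or the initiation of alternate anticancer therapy".

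One estimator is named for all of them: "The time to event data, including TTR, DR, TTP, PFS, and OS, will be evaluated using Kaplan-Meier methods". No competing-risk method appears. The Abstract (Assessment of Endpoints) repeats these rules.

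On imaging, Section 3.6 says of the on-treatment visits: "The following evaluations will be performed every 2 cycles (ie, every 6 weeks) unless otherwise indicated". After treatment stops for a reason other than progression or new therapy, scans are every 3 months. Section 5.5 ranks antitumor activity as secondary, and Section 5.2 sets the sample size by the 3+3 scheme, with no efficacy hypothesis or power.

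**The concern.** A subject who dies cannot progress afterwards. Kaplan-Meier with that death censored treats the subject as still able to progress, at the rate seen in those who remain under observation.

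For DR, a response cut short by death is therefore not counted as having ended, while PFS for the same subject ends at that death. The population is refractory to standard therapy, with a required life expectancy of 12 weeks or more and Karnofsky status of 60 or more. Deaths before a progression scan are thus plausible, though the protocol gives no figure for them.

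For TTP the risk lies in how the curve is read. One minus Kaplan-Meier is easily taken as the proportion of subjects who have progressed, and it is not that proportion when some subjects die first.

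**Working it through.** The protocol states no median, event rate or power for DR or TTP, so there is no figure of its own to reproduce. All rates below are assumptions.

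**Handling of death.** Set the rules side by side. PFS counts death and its main censoring rule requires the subject to be alive. DR and TTP do neither. A death without documented progression therefore falls under censoring at the last progression-free scan, whether or not it is also called a dropout. A responder always has a post-treatment scan, so the separate rule that censors PFS at first dose does not apply. The responder's death is a PFS event if it comes before cutoff, dropout or new therapy.

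**DR.** Let lp be the hazard of progression, ld the hazard of death without progression, and s = ld/(lp+ld) the share of DR endings that are deaths.

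- Median with death censored: ln2/lp.
- Median with death as an event: ln2/(lp+ld).
- Ratio: 1/(1−s).
- s = 0: 1.00. s = 0.10: 1/0.90 = 1.11. s = 0.20: 1/0.80 = 1.25.

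An assumed 6.0-month median with death censored becomes 5.4 months at s = 0.10 and 4.8 months at s = 0.20 when death counts.

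**TTP at 6 months.** Here s is the share of first events that are deaths, and lp+ld = ln2/(median time to first event).

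- 1−KM = 1−exp(−6·lp).
- Cumulative incidence of progression: CIF = (1−s)·(1−exp(−6·(lp+ld))).
- Median 2 months, s = 0.20: 1−KM = 0.811; CIF = 0.8 × 0.875 = 0.700; difference 0.111.
- Median 3 months, s = 0.10: 1−KM = 0.713; CIF = 0.9 × 0.75 = 0.675; difference 0.038.

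**Against sampling error.** Sections 1.4 and 2.4 report no DLTs in the first 5 cohorts, and a cohort grows to 6 only after a DLT. Evaluable numbers are then 5×3 = 15, plus 6 to 12 in Cohorts 6 and 7, plus 12 in expansion: 33 to 39, replacements aside. Take SE = √(CIF(1−CIF)/n) and pool all subjects, which is itself an assumption.

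- CIF 0.700: SE 0.080 at n = 33 and 0.073 at n = 39. The difference is 1.4 to 1.5 SE.
- CIF 0.675: SE 0.082 and 0.075. The difference is about 0.5 SE at either size.
- In a single 6-subject group the same differences are about 0.6 and 0.2 SE.

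**Direction against true progression.** A simulation of 400,000 subjects used 6-weekly scans, a 3-month median time to progression, and deaths censored at the last scan. Results at 24 weeks:

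| Assumed monthly death hazard before / after progression | 1−KM | Documented incidence | True progression |
|---|---|---|---|
| 0.05 / 0.05 | 72.1% | 62.5% | 64.8% |
| 0.02 / 0.30 | 65.9% | 55.9% | 69.1% |
| 0 / 0.30 | 65.4% | 58.4% | 72.0% |

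One minus Kaplan-Meier is above the documented incidence in every row, but below true progression in the last two.

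**The case against.** The case for leaving the text alone is substantial.

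- In this protocol, excluding death is what separates TTP from PFS, and PFS and OS are reported beside it. That stands, so the TTP definition should not change.
- Nothing in Section 5.5.3 promises a fixed-time probability of progression. Naming Kaplan-Meier does not commit the sponsor to reporting one minus the curve, and an analysis plan may settle the output. That stands, so the TTP advice is conditional on such a figure being reported.
- DR to progression alone is a choice of what to estimate, not an arithmetic error. That stands in part. The choice is legitimate, but it is not explained, and it treats the same death differently from PFS in the same section.
- DR may have few subjects or none. Section 1.4 reports no definitive tumor responses with another antibody to this receptor. That stands and limits the practical effect.
- The end-of-treatment scan, and continued scans for those who stop without progression, will catch some progression before death. They reduce the problem but do not remove it.
- No decision turns on these endpoints. The MTD rests on DLTs, and efficacy enters the choice of expansion dose only when available, beside PK, pharmacodynamic and safety data. That stands and keeps the severity low.

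**Conclusion.** The point holds in a limited, conditional form and is minor. Under the stated rules, DR looks longer than DR with death as an event whenever a responder dies without documented progression: about 11% in the median if 10% of endings are deaths, 25% if 20% are, and not at all if none are. If a probability of progression is taken from the TTP curve, it exceeds the cumulative incidence of documented progression by about 4 to 11 points at 6 months, or roughly 0.5 to 1.5 SE with 33 to 39 subjects. These sizes rest on assumed constant hazards and death shares.

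A reader might infer three stronger things that do not follow.

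- *Median TTP is too long.* Against cumulative incidence the reverse is true. With a 2-month median to first event and 20% deaths, the Kaplan-Meier median is 2/0.8 = 2.5 months. Cumulative incidence reaches 50% where 0.8(1−exp(−0.3466t)) = 0.5, at t = 2.83 months. The Kaplan-Meier median is longer only than a median that counts death, which PFS already supplies.
- *True progression is always overstated.* It can be understated when deaths follow progression that no scan has yet shown.
- *A subject's DR can outlast that subject's PFS.* It cannot. DR starts later than PFS. It ends at the same progression or, after a death, is censored at a scan no later than the PFS event.

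**What to change.** In Section 5.5.3 and the matching Abstract paragraph, define DR as the time from first documented response to documented progression or death from any cause, whichever is earlier. Censor only responders alive without progression at cutoff, dropout or new therapy, at their last progression-free scan.

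Keep TTP as defined and say explicitly that death without documented progression is not an event. Add that any probability of progression by a given time will be estimated by the Aalen-Johansen method with death as the competing event, and labelled as documented progression.

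The cost is a few sentences and a standard estimator. Survival status is already followed until death or the end of the study, so no new data are needed. The downsides are that DR may come out slightly shorter and may rest on very few responders, and that TTP probabilities become less comparable with older reports.
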